6.3.2.2 Change from Baseline to Week 12 in Severity of Pruritus or Itching

Pruritus or itching is one of the five symptoms of vulvovaginal atrophy. It is collected as described for dyspareunia in **Section 6.3.2.1** (but is applicable at all visits irrespective of sexual activity with penetration), and will be summarized and analyzed as described for vaginal dryness in **Section 6.3.1.1**. Missing values at Week 12 will be estimated using LOCF methodology. Only post-Baseline values will be carried forward.

6.3.2.3 Change from Baseline to Week 12 in Severity of Burning

Burning is one of the five symptoms of vulvovaginal atrophy. It is collected as described for dyspareunia in **Section 6.3.2.1** (but is applicable at all visits irrespective of sexual activity with penetration), and will be summarized and analyzed as described for vaginal dryness in **Section 6.3.1.1**. Missing values at Week 12 will be estimated using LOCF methodology. Only post-Baseline values will be carried forward.

6.3.2.4 Change from Baseline to Week 12 in Severity of Dysuria

Dysuria is one of the five symptoms of vulvovaginal atrophy. It is collected as described for dyspareunia in **Section 6.3.2.1** (but is applicable at all visits irrespective of sexual activity with penetration), and will be summarized and analyzed as described for vaginal dryness in **Section 6.3.1.1**. Missing values at Week 12 will be estimated using LOCF methodology. Only post-Baseline values will be carried forward.

6.3.2.5 Change from Baseline to Week 12 in Global Symptom Score 1

Global Symptom Score 1 is defined as the sum of the numerical scores of all individual symptoms (vaginal dryness; dyspareunia; pruritus or itching; burning; dysuria) for each subject at each time point: Baseline, Week 3 and Week 12 / Early Termination. The Baseline Global Symptom Score 1 will use the vaginal dryness assessment from the Screening visit and the assessments from the Baseline visit for all other symptoms.

The Global Symptom Score 1 may take the possible values ranging from 2 (at least moderate vaginal dryness as the only symptom) to 15 (all five symptoms severe in intensity) at Baseline/Screening, and possible values ranging from 0 (all symptoms absent) to 15 (all five

symptoms severe in intensity) at the Week 3 and Week 12 / Early Termination visits. The Global Symptom Score 1 will only be evaluated when all five individual symptom scores are available at a given time point.

The Global Symptom Score 1 will be summarized using descriptive statistics for continuous variables by treatment and visit. The change from Baseline value will also be summarized for all post-Baseline visits.

The mean change in Global Symptom Score 1 from Baseline to the Week 12 / Early Termination visit will be analyzed using the same parametric ANCOVA model as described for vaginal pH in **Section 6.3.1.2**. Missing values at Week 12 will be estimated using LOCF methodology. Only post-Baseline values will be carried forward.

6.3.2.6 Change from Baseline to Week 12 in Global Symptom Score 2

It is recognized that the number of missing assessments for Global Symptom Score 1 may be considerable due to its requirement for all five individual symptoms to have a response available and the dyspareunia symptom being applicable only in subjects who experienced sexual activity with penetration since the previous study visit. For this reason, the Global Symptom Score 2 is defined as an additional parameter.

Global Symptom Score 2 is defined as the sum of the numerical scores of the four individual symptoms excluding dyspareunia (vaginal dryness; pruritus or itching; burning; dysuria) for each subject at each time point: Baseline, Week 3 and Week 12 / Early Termination. The Baseline Global Symptom Score 2 will use the vaginal dryness assessment from the Screening visit and the assessments from the Baseline visit for all other symptoms.

The Global Symptom Score 2 may take the possible values ranging from 2 (at least moderate vaginal dryness as the only symptom) to 12 (all four symptoms severe in intensity) at Baseline/Screening, and possible values ranging from 0 (all symptoms absent) to 12 (all 4 symptoms severe in intensity) at the Week 3 and Week 12 / Early Termination visits. The Global Symptom Score 2 will only be evaluated when all four individual symptom scores are available at a given time point.

The Global Symptom Score 2 will be summarized using descriptive statistics for continuous variables by treatment and visit. The change from Baseline value will also be summarized for all post-Baseline visits.

The mean change in Global Symptom Score 2 from Baseline to the Week 12 / Early Termination visit will be analyzed using the same parametric ANCOVA model as described for vaginal pH in **Section 6.3.1.2**. Missing values at Week 12 will be estimated using LOCF methodology. Only post-Baseline values will be carried forward.

6.3.2.7 Change from Baseline to Week 12 in Severity of Pallor

Pallor is one of the five signs of vulvovaginal atrophy, and is recorded according to the visual inspection of the vagina as performed by the investigator at the Baseline, Week 3 and Week 12 / Early Termination visits.

Each sign will be scored by the investigator on a numeric Likert scale, as follows:

0	Absent:	The sign is not present
1	Mild:	The sign is present and is considered a mild alteration
2	Moderate:	The sign is present and is considered a moderate alteration
3	Severe:	The sign is present and is considered a severe alteration

The number and percentage of subjects with each severity of pallor at each visit will be summarized by treatment in a general summary table of signs of vulvovaginal atrophy.

The change from Baseline to Week 12 in severity of pallor may take the possible values ranging from -3 (Severe at Baseline, Absent at Week 12) to 3 (Absent at Baseline, Severe at Week 12). This endpoint will be summarized and analyzed as described for vaginal dryness in **Section 6.3.1.1**. Missing values at Week 12 will be estimated using LOCF methodology. Only post-Baseline values will be carried forward.

6.3.2.8 Change from Baseline to Week 12 in Severity of Friability

Friability is one of the five signs of vulvovaginal atrophy. It is collected and summarized as described for pallor in **Section 6.3.2.7**, and will be analyzed as described for vaginal dryness in **Section 6.3.1.1**. Missing values at Week 12 will be estimated using LOCF methodology. Only post-Baseline values will be carried forward.

6.3.2.9 Change from Baseline to Week 12 in Severity of Thinning or Flattening of Folds

Thinning or flattening of folds is one of the five signs of vulvovaginal atrophy. It is collected and summarized as described for pallor in **Section 6.3.2.7**, and will be analyzed as described for vaginal dryness in **Section 6.3.1.1**. Missing values at Week 12 will be estimated using LOCF methodology. Only post-Baseline values will be carried forward.

6.3.2.10 Change from Baseline to Week 12 in Severity of Presence of Petechiae

Presence of petechiae is one of the five signs of vulvovaginal atrophy. It is collected and summarized as described for pallor in **Section 6.3.2.7**, and will be analyzed as described for

vaginal dryness in **Section 6.3.1.1**. Missing values at Week 12 will be estimated using LOCF methodology. Only post-Baseline values will be carried forward.

6.3.2.11 Change from Baseline to Week 12 in Severity of Dry Mucosa

Dry mucosa is one of the five signs of vulvovaginal atrophy. It is collected and summarized as described for pallor in **Section 6.3.2.7**, and will be analyzed as described for vaginal dryness in **Section 6.3.1.1**. Missing values at Week 12 will be estimated using LOCF methodology. Only post-Baseline values will be carried forward.

6.3.2.12 Change from Baseline to Week 3 in Severity of Vaginal Dryness

The change from Baseline to Week 3 in vaginal dryness will be analyzed as described in **Section 6.3.1.1**. Missing values will not be imputed.

6.3.2.13 Change from Baseline to Week 3 in Severity of Dyspareunia

The change from Baseline to Week 3 in dyspareunia will be analyzed as described in **Section 6.3.1.1**. Missing values will not be imputed.

6.3.2.14 Change from Baseline to Week 3 in Severity of Pruritus or Itching

The change from Baseline to Week 3 in pruritus or itching will be analyzed as described in **Section 6.3.1.1**. Missing values will not be imputed.

6.3.2.15 Change from Baseline to Week 3 in Severity of Burning

The change from Baseline to Week 3 in burning will be analyzed as described in **Section 6.3.1.1**. Missing values will not be imputed.

6.3.2.16 Change from Baseline to Week 3 in Severity of Dysuria

The change from Baseline to Week 3 in dysuria will be analyzed as described in **Section 6.3.1.1**. Missing values will not be imputed.

6.3.2.17 Change from Baseline to Week 3 in Global Symptom Score 1

The mean change in Global Symptom Score 1, as defined in **Section 6.3.2.5**, from Baseline to Week 3, will be analyzed as described in **Section 6.3.1.2**. Missing values will not be imputed.

6.3.2.18 Change from Baseline to Week 3 in Global Symptom Score 2

The mean change in Global Symptom Score 2, as defined in **Section 6.3.2.6**, from Baseline to Week 3 will be analyzed as described in **Section 6.3.1.2**. Missing values will not be imputed.

6.3.2.19 Change from Baseline to Week 3 in Severity of Pallor

The change from Baseline to Week 3 in pallor will be analyzed as described in **Section 6.3.1.1**. Missing values will not be imputed.

6.3.2.20 Change from Baseline to Week 3 in Severity of Friability

The change from Baseline to Week 3 in friability will be analyzed as described in **Section 6.3.1.1**. Missing values will not be imputed.

6.3.2.21 Change from Baseline to Week 3 in Severity of Thinning or Flattening of Folds

The change from Baseline to Week 3 in thinning or flattening of folds will be analyzed as described in **Section 6.3.1.1**. Missing values will not be imputed.

6.3.2.22 Change from Baseline to Week 3 in Severity of Presence of Petechiae

The change from Baseline to Week 3 in presence of petechiae will be analyzed as described in **Section 6.3.1.1**. Missing values will not be imputed.

6.3.2.23 Change from Baseline to Week 12 in Severity of Dry Mucosa

The change from Baseline to Week 3 in dry mucosa will be analyzed as described in **Section 6.3.1.1**. Missing values will not be imputed.

6.3.2.24 Change from Baseline to Week 3 in Severity of Vaginal pH

The mean change in vaginal pH from Baseline to Week 3 will be analyzed as described in **Section 6.3.1.2**. Missing values will not be imputed.

6.3.2.25 Change from Baseline to Week 3 in Proportion of Superficial Cells of the Vaginal Epithelium

The mean change in proportion of superficial cells from Baseline to Week 3 will be analyzed as described in **Section 6.3.1.3**. Missing values will not be imputed.

6.3.2.26 Change from Baseline to Week 3 in Proportion of Parabasal Cells of the Vaginal Epithelium

The mean change in proportion of parabasal cells from Baseline to Week 3 will be analyzed as described in **Section 6.3.1.3**. Missing values will not be imputed.

6.3.3 Exploratory Analysis

6.3.3.1 Evaluation of Global Efficacy and Acceptability

Global efficacy is defined as the subject's perception of the effect of the study treatment on her vaginal-related symptomatology. At the Week 12 / Early Termination visit, the subject will be asked to rate the global efficacy of the treatment as highly efficacious, efficacious, non-efficacious, or detrimental.

Acceptability is defined as the subject's perception of the ease in the method of administration and the cleanliness of the product, respectively. At the Week 12 / Early Termination visit, the subject will be asked to rate the acceptability of the treatment as excellent, good, acceptable or unacceptable.

The number and percentage of subjects with each rating of global efficacy (highly efficacious, efficacious, non-efficacious and detrimental) will be summarized by treatment group and overall for the ITT population.

The number and percentage of subjects with each rating of acceptability of method of administration and cleanliness of the product (excellent, good, acceptable and unacceptable) respectively will be summarized by treatment group and overall for the ITT population.

6.3.3.2 Change from Baseline to Week 12 in Maturation Value

The maturation value for a given pathologists's analysis of a given vaginal smear slide is defined as:

$$[0.2 \times \% \text{ parabasal cells}] + [0.6 \times \% \text{ intermediate cells}] + [1 \times \% \text{ superficial cells}]$$

The maturation value for each of the two pathologists' cytologic evaluation of each vaginal smear sample will be provided by [REDACTED]. The maturation value for a given subject and visit to be used for analysis will be derived as the mean result across the two pathologists. If only one pathologist's result is available, then that result will be used to represent the overall result for that visit.

The mean change in maturation value from Baseline to Week 12 will be summarized and analyzed exactly as described for superficial cells in **Section 6.3.1.3**.

6.3.3.3 Change from Baseline to Week 3 in Maturation Value

The mean change in maturation value from Baseline to Week 3 will be analyzed as described in **Section 6.3.1.3**. Missing values will not be imputed.

6.4 Safety Analysis

Safety analysis will be performed using the Safety population. All outputs will be summarized by actual treatment received. Missing data will not be imputed.

6.4.1 Adverse Events

The assessment of safety will be based on the incidence of AEs occurring during the 12 weeks on study treatment. Adverse events will be recorded and monitored at all study visits. All AEs will be classified using the MedDRA coding dictionary. MedDRA Version 19.0 will be used, with one update during the study as per the Data Management Plan.

A treatment-emergent AE (TEAE) is defined in the study protocol as any event not present before exposure to study treatment, or any event already present that worsens in either intensity or frequency after exposure to study treatment. Events will be classified as *treatment-emergent* in the following situations:

- If the onset date of the AE is later than the date of first dose of study treatment.
- If the onset date of the AE is either unknown or is the same as the date of first dose of study treatment, and the AE is considered on the eCRF to have "onset after first dose of study drug".

- If the onset date of the AE is either unknown or is the same as the date of first dose of study treatment, and the AE is not clarified to have either “onset after first dose of study drug” or “onset before first dose of study drug” on the eCRF.
- If the onset date of the AE is partially known and it cannot be determined whether the AE started before or after the start of study treatment.

Treatment-emergent adverse events are therefore a subset of all adverse events.

The following presentations will be produced by treatment group and overall:

- A general summary table reporting the number and percentage of subjects and the number of events will be presented. The following categories will be included:
 - Subjects with no TEAEs
 - At least one TEAE
 - TEAEs leading to discontinuation of study treatment (defined as having the action taken with study treatment recorded as “drug withdrawn”)
 - Treatment-related TEAEs (defined as having the relationship to study treatment recorded as “possibly”, “probably”, “definitely” or missing)
 - Serious TEAEs
 - Serious treatment-related TEAEs
 - TEAEs leading to death (defined as having the outcome recorded as “fatal”)
- TEAEs will be summarized by SOC and preferred term. The number and percentage of subjects having each event, and the number of events will be presented. If a subject records multiple AEs with the same preferred term (i.e. with distinct start and stop dates), these shall be summarized once within the count of subject, yet each event will be counted within the number of reports of each TEAE.
- TEAEs will be summarized by SOC, preferred term and severity. The number and percentage of subjects having each severity for each event and the number of events will be presented. Any missing severity will be left as missing and categorized as such, although missing severity should be queried for completion by Data Management. If a subject has events with different severity for the same preferred term, each event will be summarized under its corresponding severity. This means that a subject may be counted across multiple severities for the same preferred term, which may result in the total number of subjects across all severities in the table appearing higher than the total number of subjects in the Safety population.

- TEAEs leading to discontinuation of study treatment will be summarized by SOC and preferred term. The number and percentage of subjects having each event, and the number of events will be presented.
- Treatment-related TEAEs will be summarized by SOC and preferred term. The number and percentage of subjects having each event, and the number of events will be presented. Any missing relationships will be left as missing and categorized as such, although missing relationships to study treatment will be queried for completion by Data Management.
- Serious TEAEs will be summarized by SOC and preferred term. The number and percentage of subjects having each event, and the number of events will be presented. Any missing serious criteria will be queried and must be completed.

Five general AE listings will be produced:

- All AEs
- Treatment-related AEs
- Serious AEs
- AEs leading to discontinuation of study treatment
- AEs leading to death

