6.3.4 Adverse Events

6.3.4.1 Definitions of Adverse Events

The investigator is responsible for reporting all adverse events (AEs) that are observed or reported during the study, regardless of their relationship to study drug or their clinical significance.

An AE is defined as any untoward medical occurrence in a subject enrolled into this study regardless of its causal relationship to study drug. An AE can, therefore, be any unfavorable and unintended sign (including an abnormal laboratory finding, for example), symptom, or disease temporarily associated with the use of a medicinal (investigational) product, whether or not considered related to the medicinal (investigational) product. Subjects will be instructed to contact the investigator at any time, after the subject gives informed consent until the end of study, if any symptoms develop.

Note that, for the purpose of this protocol, the following circumstances – with or without associated adverse event/reaction - should be included the eCRF:

- Overdose, abuse, misuse
- Off-label use
- Medication error

A treatment-emergent AE (TEAE) is defined as any event not present before exposure to study drug or any event already present that worsens in either intensity or frequency after exposure to study drug.

A serious AE (SAE) is defined as any event that:

- Results in death;
- Is immediately life-threatening;
- Requires inpatient hospitalization or prolongation of existing hospitalization;
- Results in persistent or significant disability/incapacity; or
- Is a congenital anomaly/birth defect

- Is a medically significant event

Medically significant events are defined as important medical events that may not result in death, be life-threatening, or require hospitalization but may be considered SAEs when, based upon appropriate medical judgment, they may jeopardize the subject or may require medical or surgical intervention to prevent one of the outcomes listed in this definition. Examples of such medical events include allergic bronchospasm requiring intensive treatment in an emergency room or at home, blood dyscrasias or convulsions that do not result in inpatient hospitalization, or the development of drug dependency or drug abuse.

Disability is defined as a substantial disruption of a person's ability to conduct normal life functions.

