6.3.4.2 Eliciting and Documenting Adverse Events

Adverse events will be assessed from the time the subject signs the informed consent form until exit from the study.

Events that occur prior to signing the informed consent form will be entered as medical history; AEs that have an onset after signing the informed consent will be entered on the AE form.

Subjects will be questioned and observed for evidence of AEs, whether or not related to study drug. For any pre-existing condition or abnormal laboratory finding that changes in severity after dosing, the change should be recorded as an AE. New abnormal laboratory findings that are considered clinically significant by the investigator are considered AEs.

All AEs will be collected through the Follow-up Visit (i.e. the Week 16 phone call, 4 weeks after discontinuation of study drug). Adverse event details are to be documented, including start and stop dates, whether continuous or intermittent, severity, any intervention utilized to correct the event, outcome of the event, and the relationship to the study drug.

All AEs determined by the investigator to be related to study drug must be followed until resolution, until they are considered stable, or for at least 30 days after discontinuation of study drug, whichever occurs first.

Adverse events should be classified following the Medical Dictionary for Regulatory Activities (MedDRA). Safety/PV will use the MedDRA medical dictionary to map the AE/SAE verbatim terms to specific system organ classes (SOC) and preferred terms.

Note that, for the purpose of this protocol, the following circumstances (with or without associated adverse event/reaction) should be included in the data base and will be submitted to the Sponsor, being managed in the same way and time as adverse events/reactions: any overdose (with or without associated AEs), abuse, misuse, off-label use, or medication error.

The causal relation between the investigational product and the AE will be assessed by the investigator using the following assessment criteria:

UNRELATED: This category applies to those AEs that are clearly and incontrovertibly due to extraneous causes (disease, environment, etc).

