6.3.4.4 Assessment of Severity

The severity, or intensity, of an AE refers to the extent to which an AE affects the subject’s daily activities. The intensity of the AE will be rated as mild, moderate, or severe using the following criteria:

MILD: An event that is easily tolerated by the patient, causing minimal discomfort and not interfering with everyday activities.

MODERATE: An event that is sufficiently discomforting to interfere with normal everyday activities.

SEVERE: An event that considerably restricts or prevents normal everyday activities.

Changes in the severity of an AE should be documented to allow an assessment of the duration of the event at each level of intensity to be performed. Adverse events

characterized as intermittent do not require documentation of onset and duration of each episode.

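### SAP 6.4.1 classifies treatment-emergent AEs by onset alone, so an AE that starts before first dose and worsens afterwards is left out of the TEAE tables unless the site opens a new record for the worsening

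*SAP*

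**What the plan says.** Protocol 6.3.4.1 defines a TEAE in two limbs: an event that was absent before exposure, or "any event already present that worsens in either intensity or frequency after exposure to study drug". SAP 6.4.1 restates both limbs, the second as "any event already present that worsens in either intensity or frequency after exposure to study treatment".

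SAP 6.4.1 then gives the classification rule in four situations:

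1. "If the onset date of the AE is later than the date of first dose of study treatment".
2. "If the onset date of the AE is either unknown or is the same as the date of first dose of study treatment", and the eCRF marks the event as starting after that dose.
3. The same unknown or same-day onset, with the eCRF not saying whether the event started before or after the dose.
4. "If the onset date of the AE is partially known and it cannot be determined whether the AE started before or after" treatment began.

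Three recording rules in the protocol bear on this. Section 6.3.4.2 starts AE recording at consent: "AEs that have an onset after signing the informed consent will be entered on the AE form". The same section adds: "For any pre-existing condition or abnormal laboratory finding that changes in severity after dosing, the change should be recorded as an AE". Section 6.3.4.4 says: "Changes in the severity of an AE should be documented to allow an assessment of the duration of the event at each level of intensity". It also waives the dating of individual episodes for intermittent AEs.

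SAP 6.8, which lists departures from the protocol's methods, does not mention the TEAE definition.

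**The concern.** The worsening limb is stated and then not put into operation. All four situations ask when the event began; none asks whether it became worse or more frequent after the first dose.

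Screening can last up to 30 days before the Baseline visit (Protocol 6.1.1), and AEs are recorded throughout it, so some women may reach first dose with an AE already open. If such an AE worsens on treatment and stays as one record, it keeps its pre-dose onset and meets none of the four situations, although by the protocol's definition it is treatment-emergent.

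All six planned AE summary tables (14.3.1.1 to 14.3.1.6) are restricted to TEAEs, including those for severity, discontinuation, related events and serious events. Safety and tolerability are a secondary objective of the trial. The error can only lower the counts.

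**Working it through.** The plan gives no figure to reproduce here. The check is whether the SAP rule and the protocol definition classify the same records in the same way. I applied both to six hypothetical AE records, with Day 1 as the day of first dose.

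| Record | SAP 6.4.1 rule | Protocol 6.3.4.1 definition |
|---|---|---|
| 1. Onset Day -10, worsens Day 20, one record | Not TEAE | TEAE |
| 2. Onset Day -10, no worsening | Not TEAE | Not TEAE |
| 3. Onset Day 1 marked as before the dose, worsens Day 20, one record | Not TEAE | TEAE |
| 4. Worsening on Day 20 entered as a new AE with onset Day 20 | TEAE | TEAE |
| 5. New event on Day 20 | TEAE | TEAE |
| 6. Intermittent AE from Day -10, more frequent after dosing, one record | Not TEAE | TEAE |

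The two disagree on records 1, 3 and 6, and each time the SAP under-counts. They agree on record 4, so the outcome depends on how a worsening is recorded. The recording rules, taken in turn:

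- **Protocol 6.3.4.2** has a post-dose change in severity of a pre-existing condition recorded as an AE. Section 6.3.4.3 says much the same of a medical condition present at screening that deteriorates. If that entry carries the date of the change as its onset, it meets the SAP's first situation. Neither section says what onset date the entry receives, or whether an AE that began after consent counts as a pre-existing condition.
- **Protocol 6.3.4.4** wants severity changes documented by level of intensity. Several dated records would satisfy this, and so would one record with dated severity levels. The text does not choose.
- **SAP 6.4.1** expects that a woman may have several AEs with the same preferred term and different severities, but does not say when a new one is opened.
- **Frequency** is named in the TEAE definition, but the 6.3.4.2 rule concerns severity. Because 6.3.4.4 waives episode dates for intermittent AEs, a rise in frequency need not produce any post-dose onset date.

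On scale, 280 women over four equal arms is 70 per arm. One missed woman changes an arm's incidence by 1/70 = 1.4 percentage points. The documents give neither the share of women with an AE open at first dose nor the share of those AEs that worsen, so the number missed cannot be derived.

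**The case against.** The strongest answer is that the protocol already turns worsening into a new AE. The 6.3.4.2 rule takes dosing as its reference point, so on its plain words an event that began in screening and is still open at first dose could be a pre-existing condition. Section 6.3.4.3 points the same way, and the SAP's allowance for several records per preferred term fits that practice. The eCRF completion guideline is not among the documents and may already require a split.

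This stands as far as it goes. A reader might infer that these events can never be counted, and the documents do not support that: a severity change entered with a post-dose onset is counted. Nor do they establish that severity changes are always kept within one record. What remains is that TEAE status would rest on a data-entry convention that neither document states, across about 25 sites, and that frequency lies outside the 6.3.4.2 rule.

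The consequence also has limits. Serious AEs, AEs leading to discontinuation and AEs leading to death have their own listings for all subjects (14.3.2.1 to 14.3.2.3), and all AEs and related AEs are listed as well. Burning, pruritus and dysuria are scored at Baseline, Week 3 and Week 12 and compared with placebo, so aggravation of those symptoms could show in the efficacy analyses. The events would not vanish from the report; they would be absent from the incidence tables.

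A last objection is that a worsening rule may be hard to program, because it needs dated changes and the protocol lists no dated frequency item. That is fair, and the fix allows for it.

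**Conclusion.** The concern holds in a conditional form. As written, the SAP rule does not implement the definition it quotes. An AE with onset before first dose that worsens afterwards is left out of Tables 14.3.1.1 to 14.3.1.6 unless the site opens a new AE record dated after first dose. The gap is clearest for worsening in frequency. It also applies to same-day events marked as starting before the dose, if kept as one record, and to any severity change that is not split.

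The direction is certain: the rule can only under-count. The size is not known. A reader might also infer a bias in favor of estriol. That would follow only if estriol aggravates existing events more than placebo does, which the documents do not show.

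The conclusion rests on the four situations being the complete rule, as the SAP presents them, and on no unseen guideline already requiring the split.

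**What to change.** Add a fifth situation to SAP 6.4.1: an AE with onset before first dose whose recorded intensity or frequency worsens on or after first dose is treatment-emergent, and is tabulated at its worst post-dose severity. Same-day events marked as starting before the dose should be named as included.

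To make this programmable, state in the SAP and in the eCRF completion guideline that any post-dose worsening in intensity or frequency of an AE ongoing at first dose is entered as a new AE record, with the date of worsening as its onset. The SAP's first situation then captures a worsening dated after the day of first dose, and the fifth situation covers records that were not split. Say that the same worsening is counted once.

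The cost is a sentence or two in each document. TEAE counts may rise slightly.
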